11.13.7 Safety Tables

Safety: Tables					
No.	Population	IDSL / TST ID / Example Shell	Title	Programming Notes	Deliverable [Priority]
Adverse Events (AEs)					
3.1.	All Subjects	CP_AE1p	Summary of All Adverse Events by System Organ Class	ICH E3	FSP: SAC 1
3.2.	All Subjects	CP_AE1p	Summary of All Drug-Related Adverse Events by System Organ Class	GSK CTR	FSP: SAC 1
3.3.	All Subjects	AE5	Summary of All Adverse Events by System Organ Class and Maximum Grade / Severity	ICH E3	FSP: SAC 1
3.4.	All Subjects	AE5	Summary of All Drug-Related Adverse Events by System Organ Class and Maximum Grade / Severity	GSK CTR	FSP: SAC 1
3.5.	All Subjects	AE15	Summary of Common (>=10%) Non-serious Adverse Events by System Organ Class and Preferred Term (Number of Subjects and Occurrences)	FDAAA, EudraCT	FSP: SAC 1
Cytokine Release Syndrome (CRS) Events					
3.6.	All Subjects	SAFE_T2 (Also see GSK2245035 TL7116958 idsfinal Table 10.104)	Summary of Cytokine Release Syndrome Events	Create two versions of the Table within the output. The 1 st uses the Main Treatment descriptors and the 2 nd uses the Alternative Treatment descriptors (Pbo P, Pbo U, 20ng P, 20ng U).	SAC 1

Safety: Tables					
No.	Population	IDSL / TST ID / Example Shell	Title	Programming Notes	Deliverable [Priority]
3.7.	All Subjects	SAFE_T3 (Also see GSK2245035 TL7116958 idslfinal Table 10.105)	Summary of the Consistency of Cytokine Release Syndrome Events Reporting by Individuals over Dosing Visits	Create two versions of the Table within the output. The 1 st uses the Main Treatment descriptors and the 2 nd uses the Alternative Treatment descriptors (Pbo P, Pbo U, 20ng P, 20ng U). Sort by CRS Category, Treatment Add footnotes about set interval notation for category boundaries	SAC 1
Serious and Other Significant Adverse Events					
3.8.	All Subjects	CP_AE1p	Summary of Serious Adverse Events by System Organ Class	Only produce if more than 5 events IDSL / GSK CTR	FSP: SAC 1
3.9.	All Subjects	CP_AE1p	Summary of Drug-Related Serious Adverse Events by System Organ Class	Only produce if more than 5 events GSK CTR	FSP: SAC 1
Laboratory: Chemistry					
3.10.	All Subjects	LB1	Summary of Chemistry Changes from Baseline	ICH E3 Include (absolute) Baseline values summarised as a row in the table and then the change from baseline for each visit below. Do not include Screening visit 1 values	FSP: SAC 2
3.11.	All Subjects	LB4	Summary of Emergent Chemistry Results by Normal Range Criteria	ICH E3 Planned times should be each post-visit timepoint (e.g. DV1 24h, DV8 pre-dose, DV8 24h). Do not include screening visit 1 values. Use Normal Ranges for Lab tests rather than PCI ranges to determine criteria.	FSP: SAC 2

Safety: Tables					
No.	Population	IDSL / TST ID / Example Shell	Title	Programming Notes	Deliverable [Priority]
Laboratory: Haematology					
3.12.	All Subjects	LB1	Summary of Haematology Changes From Baseline	ICH E3 As per Lab Chemistry equivalent	FSP: SAC 2
3.13.	All Subjects	LB4	Summary of Emergent Haematology Results by Normal Range Criteria	ICH E3 As per Lab Chemistry equivalent	FSP: SAC 2
Laboratory: Hepatobiliary (Liver)					
3.14.	All Subjects	LIVER1	Summary of Liver Monitoring/Stopping Event Reporting	IDSL	FSP: SAC 2
ECG					
3.15.	All Subjects	EG1	Summary of ECG Findings	IDSL	FSP: SAC 2
3.16.	All Subjects	EG2	Summary of Change from Baseline in ECG Values by Visit	IDSL Include (absolute) Baseline values as the first record. Do not include Screening visit 1 values	FSP: SAC 2
Vital Signs					
3.17.	All Subjects	VS1	Summary of Change From Baseline in Vital Signs by Visit	ICH E3 Include (absolute) Baseline values as the first record. Do not include Screening visit 1 values	FSP: SAC 2
Medications					
3.18.	All Subjects	CP_CM1	Summary of Concomitant Medications by Generic Term		FSP: SAC 2
Rescue Medication					
3.19.	All Subjects	Table 10.112 TL7116958	Summary of Rescue Medication Usage	Include reasons (if easily condensed to a handful of terms). Exclude any rescue medication given as part of the BAC procedure(s) and add this as an explanatory footnote.	FSP: SAC 2

Safety: Tables					
No.	Population	IDSL / TST ID / Example Shell	Title	Programming Notes	Deliverable [Priority]
PEF					
3.20.	All Subjects	EFF_T1	Summary of Weekly Maximum PEF by Visit	Calculate the maximum PEF for the week per subject Add Appropriate Visit Column to Shell	FSP: SAC 2
3.21.	All Subjects	EFF_T1	Summary of Weekly Weighted Mean PEF by Visit	Add Appropriate Visit Column to Shell	FSP: SAC 2
Nasal Examination					
3.22.	All Subjects	SAFE_T1	Summary of Nasal Examination Data by Visit	Count as yes any entries in the free text field for Signs of Bleeding.	FSP: SAC 2
3.23.	All Subjects	SAFE_T4	Shift Tables of Nasal Examination Status from Pre-Dose DV1 to 24h Post Dose DV8	Count as yes any entries in the free text field for Signs of Bleeding. Separate page per category/domain	FSP: SAC 2

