### 3. OBJECTIVE(S) AND ENDPOINT(S)

#### Objective(s)/Endpoint(s)

[figure not shown]
Objectives	Endpoints
Primary	

 
To evaluate the effect of treatment with i.n. GSK2245035 compared to placebo on the allergen-induced late asthmatic response (LAR) in subjects with allergic asthma.
 
	
 
LAR: minimum FEV1 between 4-10 hours following allergen challenge one week after treatment.
 
LAR: weighted mean FEV1 between 4-10 hours following allergen challenge one week after treatment.
 

Secondary	

 
To evaluate the effect of treatment with i.n. GSK2245035 compared to placebo on the allergen-induced early asthmatic response (EAR) in subjects with allergic asthma.
 
	
 
EAR: minimum FEV1 between 0-2 hours following allergen challenge one week after treatment.
 
EAR: weighted mean FEV1 between 0-2 hours following allergen challenge one week after treatment.
 

 
Safety
 
	

 
To evaluate the safety and tolerability of treatment with eight weekly doses of 20 ng i.n. GSK2245035
 
	
 
General safety endpoints including AE, peak expiratory flow (PEF), rescue salbutamol use, and clinical laboratory parameters
 

Objectives	Endpoints

 
• Exploratory
 
	

 
• To evaluate the duration of effect of treatment with i.n. GSK2245035 compared to placebo on the allergen-induced asthmatic responses (LAR and EAR) in subjects with allergic asthma.
 
	
 
• LAR: minimum and weighted mean FEV1 between 4-10 hours following allergen challenge approximately 4 and 12 weeks after treatment.
 
• EAR: minimum and weighted mean FEV1 between 0-2 hours following allergen challenge approximately 4 and 12 weeks after treatment.
 

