#### **7.4.7. PEF monitoring**

Subjects will be given a PEF peak flow meter at screening, along with a diary card. This will be used for safety monitoring after the BACS. Subjects will record their PEF readings each morning and evening onto the diary card every day from the start of study treatment on DV 1 until the 4 week follow-up visit.

The subject will be instructed to contact the investigator if at any time during the study the PEF measurements go outside the normal range for the subject. These instructions will be clearly printed on the diary card.

All information from the diary card will be transcribed into the eCRF.

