8.2.3 Overview of Planned Other Safety Analyses

The safety analyses will be based on the All Subjects Population, unless otherwise specified.

Table 9 provides an overview of the planned analyses, with further details of data displays being presented in [Appendix 13](#): List of Data Displays.

Table 9 Overview of Planned Other Safety Analyses

Endpoint	Absolute			Change from BL		
	Summary		Individual	Summary		Individual
	T	F	L	T	F	L
ECG						
ECG Findings	Y					
Change from Baseline in ECG Values by Week				Y		
All ECG Values for Subjects with a Value of PCI			Y			
ECG Values of PCI			Y			
Abnormal ECG Findings			Y			
Vital Signs						
Change From Baseline in Vital Signs by Week				Y		
All Vital Signs for Subjects with a Value of PCI			Y			
Vital Sign Values of PCI			Y			
Rescue Salbutamol Medication (excluding that given as part of BAC procedure)						
Rescue Medication usage	Y		Y			
Peak Expiratory Flow (PEF)						
Mean PEF Profiles		Y	Y			
Mean Morning PEF Profiles		Y	Y			
Mean Evening PEF Profiles		Y	Y			
Weekly Maximum PEF	Y		Y			
Weekly WM PEF	Y		Y			
Nasal Examination						
Frequency of Abnormalities	Y		Y			

NOTES:

- T = Table, F = Figures, L = Listings, Y = Yes display generated, PCI = Potential Clinical Importance
- Summary = Represents TFL related to any summaries (i.e. descriptive statistics) of the observed raw data.
- Individual = Represents FL related to any displays of individual subject observed raw data.

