11.5 Appendix 5: Derived and Transformed Data

11.5.1 General

Multiple Measurements at One Time Point

 Generally, mean of the measurements will be calculated, unless replicate FEV₁ or PEF measurements exist in which case the maximum will be utilised, and used in any derivation of summary statistics but if listed, all data will be presented. If there are two values within a time window the value closest to the target day for that window will be used. If values are the same distance from the target then the mean will be taken. Subjects having both High and Low values for Normal Ranges at any post-baseline visits for safety parameters will be counted in both the High and Low categories of 'Any visit post-baseline' row of related summary tables. This will also be applicable to relevant Potential Clinical Importance summary tables.
Study Day

 Calculated as the number of days from randomisation date : 
 Ref Date = Missing → Study Day = Missing Ref Date < Randomisation Date → Study Day = Ref Date – Randomisation Date Ref Date ≥ Randomisation Date → Study Day = Ref Date – (Randomisation Date) + 1

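### The PEF tables give only weekly maxima and weighted means of absolute values, so no table or figure shows short individual falls by arm

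*SAP*

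**What the plan says.** The protocol's objectives table names PEF among the safety endpoints: "General safety endpoints including AE, peak expiratory flow (PEF), rescue salbutamol use, and clinical laboratory parameters". Protocol 7.4.7 sets the collection: "Subjects will record their PEF readings each morning and evening onto the diary card every day", from the first dosing visit to the 4-week follow-up visit. It gives the purpose as "This will be used for safety monitoring after the BACS" (BAC is the bronchial allergen challenge). It also provides a live safeguard: "The subject will be instructed to contact the investigator if at any time during the study the PEF measurements go outside the normal range", judged against the subject's own range.

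The SAP reports PEF as follows.

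- **Tables.** Table 3.20 carries the programming note "Calculate the maximum PEF for the week per subject". Table 3.21 is "Summary of Weekly Weighted Mean PEF by Visit". Table 9 in SAP 8.2.3 lists "Weekly Maximum PEF" and the weekly weighted mean under absolute values only. ECG and vital signs, in the same table, do have change-from-baseline summaries.
- **Figures.** Figures 3.1-3.3 (SAP 11.13.8) plot raw treatment means for each day with confidence bands, for overall, morning and evening PEF.
- **Listing.** Listing 66 (SAP 11.13.16) gives PEF by study day, with the weekly maximum and weighted mean added.
- **Replicates.** SAP 11.5.1 averages repeat measurements at a time point, "unless replicate FEV₁ or PEF measurements exist in which case the maximum will be utilised".
- **Baseline.** SAP 11.4.2.1 has no PEF row, but its general default is the last assessment before dosing. SAP 11.4.2.2 defines change and percentage change from baseline. No PEF display calls on either.

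**The concern.** PEF is collected to catch airflow worsening after an allergen challenge, and such worsening may be brief and confined to a few subjects. The summary should therefore respond to low readings. A weekly maximum responds to the best reading of the week. A weekly mean spreads a bad day over seven. Neither is set against the subject's own starting level, although the protocol's safeguard judges PEF within the subject.

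At stake is what the safety section of the report can say. If the two PEF tables look alike across arms, that says little about whether more subjects on one arm had short falls. A reader would have to work through the listing to find out, and no planned output would summarise the answer by arm.

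**Working it through.** The documents give no planned difference, SD or power for PEF, so there is no figure of the plan's to reproduce. The check asks how each planned summary responds to a known fall in one subject.

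**Inputs**

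- Two readings a day over 7 days: 14 a week (Protocol 7.4.7).
- Weekly maximum: the largest of the 14 (Table 3.20).
- Weekly weighted mean: the SAP gives no PEF formula. I assume the weekly TNSS rule in SAP 11.5.6: average the morning and evening values, then apply the linear trapezoid over days 1 to 7 and divide by 6. The weights are 1/12 for days 1 and 7 and 1/6 for each of days 2 to 6, which sum to 1.
- About 24 randomised and 20 completers per arm (Protocol 4.2, 4.3).
- Assumed falls of 20% to 40%, with PEF otherwise constant.

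**Formulas.** For a fall f on whole days with total weight w, the weighted mean changes by -f × w. A single reading counts half, because the day's value is the mean of two. The maximum changes by 0 while any reading stays normal. The minimum changes by -f.

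**Results for f = 30%**

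| Pattern in one subject | Weekly maximum | Weekly weighted mean | Weekly minimum |
|---|---|---|---|
| One reading, mid-week | 0% | 0.5 × 0.30 × 1/6 = -2.5% | -30% |
| Whole day, day 7 | 0% | 0.30 × 1/12 = -2.5% | -30% |
| Whole day, mid-week | 0% | 0.30 × 1/6 = -5% | -30% |
| Two interior days | 0% | 0.30 × 2/6 = -10% | -30% |
| Three interior days | 0% | 0.30 × 3/6 = -15% | -30% |
| Days 1 to 6 | 0% | 0.30 × 11/12 = -27.5% | -30% |

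Over falls of 20% to 40%, one mid-week day gives -3.3% to -6.7% in the weighted mean. The maximum stays at 0% even for a 40% fall on six of the seven days.

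**Daily figures.** If one subject of 24 falls 30% for a day, and subjects have similar PEF, that day's arm mean moves by 30%/24 = 1.25% (30%/20 = 1.5% with 20 subjects). If six subjects each fall on a different day, no day's mean moves by more than that. If the whole arm falls on the same day, the mean moves by the full 30%.

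**Reading noise.** I simulated independent readings with an assumed coefficient of variation of 5% or 8%. In a week with no fall, the minimum averages 0.915 or 0.864 of the usual level. With a one-day 30% fall it averages 0.680 or 0.668. The maximum barely changes (1.085 to 1.081, and 1.136 to 1.130), and the weighted mean goes from 1.000 to 0.950 in both cases. The minimum therefore still separates the two weeks, but it sits below the usual level even in a quiet week and needs a comparison between arms.

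**The case against.** The strongest reply is that PEF is reported in more places than two tables, and that PEF is not the only route by which worsening airflow would be seen.

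- Figures 3.1-3.3 are daily. A fall shared by an arm on the same day would appear at full size, and challenge days line up across subjects as far as visits keep to schedule.
- Listing 66 shows PEF by study day. With about 48 subjects, individual falls can be found by inspection.
- Table 3.21 does register a fall, though diluted.
- Subjects call the investigator when PEF leaves their range. Wheeze, chest tightness and cough are listed as disease-related events. Rescue use is tabulated (Table 3.19). A Safety Review Team with an external expert reviews data during the study.
- A minimum of unsupervised home readings can be set by one poor effort.

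All of this stands. It rules out several stronger readings that might be inferred:

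- *That PEF falls leave no trace in the report, or that an absence of PEF signal would be uninformative.* The figures, the listing and the weighted mean contradict this.
- *That PEF has no baseline.* A default rule exists; what is missing is a display that uses it.
- *That absolute arm means are too imprecise because PEF varies so much between subjects.* Neither document gives a PEF SD, and randomisation keeps the comparison unbiased.
- *That subjects are left unprotected.* The live safeguard is a separate matter from the analysis.

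The reply does not supply a summary, by arm, of how far individual subjects fell. The mock shells are in a separate document. If the shell for Table 3.20 includes a minimum across subjects, it would be the smallest of the weekly maxima, not a weekly minimum.

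**Conclusion.** The point holds as a gap in the safety summaries. No planned table or figure gives a weekly minimum PEF, a change from baseline or each subject's largest fall by arm. Short individual falls are identifiable mainly from Listing 66.

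The maximum's insensitivity follows from its definition and needs only one reading at the usual level. The dilution in the weighted mean, threefold for two interior days and sixfold for one mid-week day, rests on borrowing the TNSS formula and on otherwise constant PEF. The fall sizes are illustrative and are not estimates for this drug or this challenge. Nothing here touches the primary analysis or the live monitoring of subjects. It is a cheap improvement to the reporting of a named safety endpoint.

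**What to change.** 1. Add weekly minimum PEF to Table 3.20, alongside the weekly maximum or in its place, and keep the weighted mean beside it so that a single poor effort can be recognised.
2. Tabulate change from baseline by week, and each subject's largest percentage fall by arm, using the SAP's default baseline. The sponsor should confirm that the Day 1 morning PEF is taken before dosing: Protocol 7.3.4 states this for TNSS, but 7.4.7 does not for PEF. That baseline may be a single reading, which should be footnoted.
3. State the formula for the weekly weighted mean PEF.
4. Show separately the diary days after the challenge at follow-up visit 1, and the roughly 24 hours after the challenge at follow-up visit 2 before the diary is returned. Diary PEF starts at the first dosing visit and ends at the 4-week visit, so it does not cover the screening challenge or the one at follow-up visit 3.

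No new data are needed. The cost is a little extra programming, plus the minimum's sensitivity to poor efforts. No PEF threshold or clinical rule is proposed; any such choice belongs to the sponsor.

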	
considered to be adverse, nasal irritancy [GlaxoSmithKline Document Number 2010N110564_04].
 
GSK2245035 has been previously tested in subjects with allergic rhinitis with or without mild asthma at the same dose (20 ng) and the same i.n. regimen (8 weekly administrations) proposed for this study.
 
I.n. GSK2245035 induced transient dose related increases in body temperature (GSK2245035 80 ng maximum 1.37°C; GSK2245035 20 ng group maximum 0.34°C).
 
I.n. GSK2245035 induced dose related increases in the frequency and severity of AEs possibly related to cytokine induction. Headache was the most frequently reported cytokine related AE for all treatments (79% subjects in GSK2245035 80 ng, 29% subjects in GSK2245035 20 ng and 21% subjects in placebo group), including mild, moderate and severe reports.
 
Fever was a frequently reported cytokine related AE at GSK2245035 80 ng (58%) while no reports of cytokine related fever were noted at GSK2245035 20ng or
	

Potential Risk of Clinical Significance	Summary of Data/Rationale for Risk	Mitigation Strategy
	
placebo. Cytokine related fever mainly emerged after the second dosing visit; most cytokine related fever occurred within 12 hours of dosing.
 
One subject receiving GSK2245035 80ng was withdrawn due to severe myalgia occurring after the second dose. One GSK2245035 20ng subject reported myalgia and arthralgia of moderate severity.
 
At both doses cytokine related AEs were self resolving with a median duration of approximately <math>\leq</math> 1 day.
 
No severe cytokine related events were reported at GSK2245035 20ng.
 
There were no reports of vomiting, diarrhea or hypotension in any treatment group.
	
Nasal irritancy	
Nasal irritancy was noted in rats and monkeys after repeat intranasal dosing; the effects in the rat were seen only at very high dose levels/concentrations (Section 4.5 of the Investigator Brochure (IB)) [GlaxoSmithKline Document Number 2010N110564_04].
 
The finding from the rat and monkey studies
	Thorough monitoring of nasal AEs will be performed throughout the treatment period to allow early mitigation of risk. Nasal examinations will be performed pre-dose and 24 hours post-dose on dosing visits 1 and 8.

Potential Risk of Clinical Significance	Summary of Data/Rationale for Risk	Mitigation Strategy

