### 5.4. Withdrawal/Stopping Criteria

Reasons for withdrawal from the study may include:

- Use of a prohibited medication that cannot be safely discontinued while maintaining the subject's health.
- Treatment code is unblinded.
- Pregnancy: Any female subject who becomes pregnant.

The following actions must be taken in relation to a subject who fails to attend the clinic for a required study visit:

- The site must attempt to contact the subject and re-schedule the missed visit as soon as possible.
- The site must counsel the subject on the importance of maintaining the assigned visit schedule and ascertain whether or not the subject wishes to and/or should continue in the study.
- In cases where the subject is deemed 'lost to follow up', the investigator or designee must make every effort to regain contact with the subject (where possible, 3 telephone calls and if necessary a certified letter to the subject's last known mailing address or local equivalent methods). These contact attempts should be documented in the subject's medical record.
- Should the subject continue to be unreachable, only then will he/she be considered to have withdrawn from the study with a primary reason of "Lost to Follow-up".

A subject may withdraw from study treatment at any time at his/her own request, or may be withdrawn at any time at the discretion of the investigator for safety, behavioural or administrative reasons. If a subject withdraws from the study, he/she may request destruction of any samples taken, and the investigator must document this in the site study records.

Subjects withdrawn from the study while already exposed to IP will be asked to complete all safety assessments as outlined in the Time and Events Table (Section 7.1.2). Relevant pages of the case report form (CRF) should be completed by the investigator.

The replacement of withdrawn subjects will be at the discretion of the sponsor. If a subject misses one treatment dose, the investigator will consult with the GSK medical monitor as to whether the subject can receive further treatment. If more than one treatment dose is missed, then the subject may be withdrawn from the study, at the discretion of the Sponsor, in consultation with the investigator.

If subjects prematurely discontinue the study, additional replacement subjects may be recruited and assigned the next available randomisation number, at the discretion of the Sponsor, in consultation with the investigator.

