### 7.1.2. Time and Events Table – Dosing visit (DV) 1 (Day 1) – DV8 (Week 8) and Early Withdrawal Visit (EW)

Procedure	Pre-dose	Dose	Post-dose				Early- Withdrawal	Notes
		0 hour	20 mins	1 hour	12 hours	24 hours		
Outpatient visit		X				X	X	Subjects get discharged 1-2 hours after dosing.
Inclusion and exclusion criteria/eligibility review	X							Only on DV1
Diary card collection and review		X					X	Collect and review diary card at every dosing visit
AE/SAE review		X					X	
Concomitant medication review		X					X	
12-lead ECG	X			X		X	X	Perform on DV1 and DV8 only. Not required at EW if this occurs during FU
Vital signs (including temperature)	X 			X 		X 	X	 Perform on DV1-8  Perform on DV1, 4 and DV8 only. Not required at EW if this occurs during FU
Laboratory assessments (include liver chemistries, haematology, clinical chemistry and urinalysis)	X					X	X	Collect samples for laboratory assessments on DV1 and DV8, Not required at EW if this occurs during FU
Blood sample for PK analysis	X		X	X				Collect samples on DV1, DV4 and DV8
Genetic sample		X						Take one sample on any of the dosing visits after genetics consent.
FeNO measurement	X							Perform FeNO measurements pre-dose on all dosing visits 1-8
Nasal examination	X					X		Conducted pre-dose at all study visits and 24 hours post-dose on DV1, DV4 and DV8

Procedure	Pre-dose	Dose	Post-dose				Early-Withdrawal	Notes
			0 hour	20 mins	1 hour	12 hours		
Nasal lavage	X						X	Collect nasal lavage samples pre-dose and 24hrs post-dose on DV1, DV4 and DV8
Blood sample for biomarker analysis	X						X	Collect blood for serum samples and PBMC preparations pre-dose and 24 hrs post-dose on DV1 and DV8
Blood sample for RNA analysis	X 						X 	PAX-gene tubes for TLR7/AFFY chip gene expression in blood collected pre-dose on DV1  and 24 hrs after DV8 
Call RAMOS	X							Randomisation will occur is at Visit 1 via the IRT. Sites should also call RAMOS at DV5.
Dispensing of study medication	X							One device will be assigned on DV1. The second device will be assigned on DV5. All devices remain in the unit.
Study drug administration		X						All doses are administered in the unit.

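### The nasal examination shift table (SAP Table 3.23) uses one fixed end point, 24 h after dose 8, so it cannot classify subjects who stop earlier and misses abnormalities that clear by then.

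*SAP*

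**What the plan says.** **The risk.** Protocol 4.6.1 lists two risks of the investigational product, cytokine-related events and nasal irritancy. On the second it says "Nasal irritancy was noted in rats and monkeys after repeat intranasal dosing". Its mitigation is "Thorough monitoring of nasal AEs will be performed throughout the treatment period to allow early mitigation of risk", plus nasal examinations.

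**The schedule.** In Protocol 7.1.2 the nasal examination row is marked at pre-dose and at 24 h, with the note "Conducted pre-dose at all study visits and 24 hours post-dose on DV1, DV4 and DV8". The Early-Withdrawal cell of that row is blank. The diary card, AE/SAE, concomitant medication, ECG, vital signs and laboratory rows are all marked there. The follow-up table (7.1.3) has no nasal examination row. Under Protocol 5.4, withdrawn subjects who have been dosed "will be asked to complete all safety assessments as outlined in the Time and Events Table", with reference to 7.1.2, so the blank cell governs. Protocol 4.6.1 gives different times: "Nasal examinations will be performed pre-dose and 24 hours post-dose on dosing visits 1 and 8".

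**The displays.** SAP 11.13.7 has two nasal examination tables, both on All Subjects. Table 3.22 is "Summary of Nasal Examination Data by Visit" and Table 3.23 is "Shift Tables of Nasal Examination Status from Pre-Dose DV1 to 24h Post Dose DV8". Listing 67 (SAP 11.13.16) shows individual examinations, including unscheduled ones. SAP 11.6.1 keeps withdrawn subjects' planned data in summary tables. SAP 11.4.3 sends unplanned readings to listings and keeps unscheduled visits out of tables and figures.

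**The concern.** A shift table answers the question a safety reader asks about local tolerability: of those whose nose was normal before the first dose, how many became abnormal on treatment? Table 3.23 answers it at a single late time. That leaves two gaps.

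- A subject who stops before DV8 + 24 h has no end value, and the SAP text has no rule for classifying that subject.
- A subject who is abnormal in mid-treatment and normal again at DV8 + 24 h is shown as unchanged.

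The blank early-withdrawal cell adds to the first gap. If irritation develops after the last planned examination, no examination is scheduled to record it when the subject leaves, and one done ad hoc would be listed but not tabulated. What is at stake is how complete one descriptive table is for a named product risk. The primary analysis is not affected.

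**Working it through.** No sample size, power or error rate is stated for nasal examination, so the plan has no figure to reproduce. The check is a count of examinations, followed by simple proportions.

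**1. Examinations planned and used.** I read the 7.1.2 note as covering all eight dosing visits.
- Planned: 8 pre-dose + 3 at 24 h (DV1, DV4, DV8) = 11.
- After the first dose: 11 − 1 (DV1 pre-dose) = 10.
- Used as an end point in Table 3.23: 1 (DV8 + 24 h). The other 10 − 1 = 9 planned post-baseline examinations do not enter the shift.

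**2. Is there a planned examination after the last dose?** Take a subject who stops after dose k and does not attend the next dosing visit.

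| Last dose k | Planned examination after it (7.1.2 times) | End value in Table 3.23 |
|---|---|---|
| 1, 4 | yes, at 24 h | no |
| 2, 3, 5, 6, 7 | none | no |

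So 5 of 7 stopping points have no planned examination after the last dose. Under the times in 4.6.1 only k = 1 has one, which makes 6 of 7. A subject who attends the next dosing visit and is examined pre-dose before being withdrawn does have one under 7.1.2, and it enters Table 3.22.

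**3. How far Table 3.23 could move.** Protocol 4.2 randomises about 24 per arm and 4.3 wants 20 completers: 24 − 20 = 4, and 4/24 = 16.7%. This is only a rough ceiling for missing end values. Completers must also finish the one-week follow-up allergen challenge, replacements are allowed, and no dropout rate is stated.

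Assumption: w of 24 in an arm stop for irritancy, w = 0 to 4; each would have been abnormal if examined; nobody else is missing or abnormal.

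| w | Subjects with a DV8 + 24 h value: 0/(24 − w) | All treated: w/24 |
|---|---|---|
| 0 | 0/24 = 0% | 0.0% |
| 1 | 0/23 = 0% | 4.2% |
| 2 | 0/22 = 0% | 8.3% |
| 3 | 0/21 = 0% | 12.5% |
| 4 | 0/20 = 0% | 16.7% |

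The direction is not fixed. With 2 abnormal completers:
- 4 withdrawals, all for irritancy: 2/20 = 10.0% against (2 + 4)/24 = 25.0%, so the table understates.
- 4 withdrawals, none affected: 2/20 = 10.0% against 2/24 = 8.3%, so the table overstates.

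**4. What still records an early stopper.** Table 3.22 does, up to the last planned examination; so does Listing 67. AE review is marked at early withdrawal, so a reported nasal event reaches AE Tables 3.1 to 3.4 and Listing 13, and Listing 22 if it led to withdrawal.

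**The case against.** A reader might infer that subjects who stop for irritancy disappear from the irritancy result. They do not, as step 4 of the working shows. A reader might also infer that Table 3.23 can only understate irritancy. The last example in step 3 shows that it can overstate when withdrawals are unrelated. Both objections stand, and the point made here relies on neither inference.

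Other fair objections:
- *Low materiality.* Table 3.23 is one descriptive table with second delivery priority, in a study without formal hypotheses. Protocol 4.6.1 reports good local tolerability in clinical studies of up to 8 weeks, and Protocol 7.4 provides for ongoing safety review and added safety time points. This stands, and it limits the weight of the point.
- *The mock shell.* The layout for Table 3.23 (SAFE_T4) is in a separate document that was not available. It may carry a missing category. The SAP text gives no rule.
- *The timing mismatch is editorial.* Protocol 7 and 7.3.5 both defer to the Time and Events Table, and Appendix 7 shows that examinations on DV1 and DV8 were the schedule before Amendment 2. So 4.6.1 looks like a leftover, and it does not itself distort Table 3.23.

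The remaining gap is not answered. Table 3.22 gives frequencies by visit, not change within a subject, and an AE report does not replace the physician's examination that 7.3.5 sets up to look for irritancy.

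**Conclusion.** The point holds as a cheap improvement to one safety display. Three facts carry it: Table 3.23 has a single end point at DV8 + 24 h; no nasal examination is marked at early withdrawal; and an unplanned one would not be tabulated. In consequence early stoppers cannot be classified, transient abnormalities are not seen, and at 5 of 7 stopping points no planned examination follows the last dose, provided the next dosing visit is not attended.

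Neither the direction nor the size of any distortion can be stated. The numbers in step 3 rest on assumed reasons for withdrawal and show only a possible range. The documents do not support saying that these subjects are lost to the irritancy data, or that the table is biased in a known direction.

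The SAP already takes more care with the other product risk. For cytokine-related events, SAP 11.5.3 takes the highest grade where several terms fall in one category and relates event counts to dosing visits actually attended. Figure 3.4 footnotes subjects who did not complete all eight visits, and Listing 17 says how to show early withdrawals.

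**What to change.** 1. **SAP Table 3.23.** Add a panel shifting from DV1 pre-dose to the worst post-baseline examination, for all dosed subjects with any post-baseline examination. Include planned, unscheduled and early-withdrawal examinations, and state this as an exception to the rule on unscheduled data in SAP 11.4.3. Keep the existing DV8 + 24 h panel, with a category for subjects who have no examination at that time, so that every dosed subject is accounted for.
2. **Protocol 7.1.2.** Mark nasal examination in the Early-Withdrawal column.
3. **Protocol 4.6.1 and 7.1.2.** Reconcile the examination times.

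The cost is one brief visual check at a visit already attended, one extra table panel drawn mostly from examinations already planned, and one text correction. A worst-value panel gives subjects with more examinations more chances to show an abnormality, so it should be read beside the fixed-time panel and not replace it.
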